#### **5.2.6 30 DAY POST DISCHARGE/WITHDRAWAL FOLLOW-UP**

Subjects will receive a follow-up phone call from a study coordinator and Medical Charts will be reviewed to assess if the subject was readmitted within 30 days of discharge. Follow-up phone call and Medical Chart review will instead occur 30 days after withdrawal for patients who are withdrawn prior to discharge.

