## **9. STATISTICAL ANALYSIS & DATA MANAGEMENT**

Continuous variables will be reported as means  $\pm$  standard deviations or medians [quartile 1, quartile 3], if skewed. Categorical variables will be reported as frequencies and percentages.

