## **8.7. Statistical Considerations**

### **a. Study Design Endpoints**

Primary and secondary endpoints include the number of in-hospital PRN respiratory therapy treatments, time in between PRN respiratory therapy, change in peak inspiratory flow rate measured with an InCheck DIAL through medium low resistance from baseline to discharge, length of stay, at-home drug compliance, 30-day re-admissions (all-cause and respiratory), 30-day survival, cost of respiratory therapy, and QOL score.

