### **c. Analysis of Primary Endpoint**

The number of PRN respiratory treatments during hospitalization will be reported as the median [quartile 1, quartile 3] and as the average number of PRN respiratory treatments per inpatient day  $\pm$  standard deviation. A comparison between patients who were and were not readmitted within 30-days will be made using a Wilcoxon signed rank test for the number of PRN respiratory treatments. Additionally, the incident rate ratio of the average per-inpatient

day PRN treatments will be estimated using a robust Poisson regression model comparing patients who were readmitted within 30-days to those who were not.

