#### **d. Analysis of Secondary Endpoints**

Time (in days) in between PRN treatments, change in respiratory inspiratory flow rate from baseline to discharge, length of stay, at-home drug compliance, 30-day readmissions (all-cause and COPD/Asthma exacerbation), and 30-day survival will be compared between patients who were and were not readmitted using t-tests or chi-square tests (or Wilcoxon Rank Sum tests and Fisher's Exact tests), as appropriate.

The efficacy of the treatment protocol in the study cohort compared to the historical cohort will be assessed by comparing (1) the average number of PRN treatments per patient day while hospitalized estimated using a robust Poisson regression model (2) length of stay in the hospital, and (3) the rate of rehospitalization, using the Wilcoxon Rank sum test.

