#### **e. Reporting and Exclusions**

Missing data will not be imputed or carried forward in any of the analyses.

The sample size for continuous variables will be the number of subjects with non-missing data; in the summary of categorical variables, subjects with missing data will be excluded in the calculation of percentages.

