## **9.2 Informed Consent**

The investigator or delegated person must explain to each subject the nature of the study, its purpose, the procedures involved and any discomfort it may entail. Each subject must be informed that participation in the study is voluntary, that he/she may withdraw from the study at any time, and that withdrawal of consent will not affect his/her subsequent medical treatment or relationship with the treating physician.

The informed consent should be given by means of a standard written statement, written in nontechnical language. The subject should read and consider the statement before signing and dating it and should be given a copy of the signed document. No subject can enter the study before his/her informed consent has been obtained. The ICF must be submitted by the Investigator for IRB approval.

There will also be an option to do electronic consenting and electronic signatures by using study approved methods such as hospital telehealth system, patient iPad, telephone calls/telephone video conferencing. Documents will be sent electronically to the email address you provide for you to review the documents and sign off on.

A telephone call will be made by an authorized study research staff member to assess if the subject was readmitted within 30 days of discharge.

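### Section 8.7 names a paired (signed rank) test for two independent groups, and tests 30-day readmission between groups defined by readmission

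*Combined protocol and SAP*

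**What the plan says.** Section 8.7.c (Analysis of Primary Endpoint) first summarises the number of in-hospital PRN treatments descriptively, then adds a test: "A comparison between patients who were and were not readmitted within 30-days will be made using a Wilcoxon signed rank test". It also plans a robust Poisson model for the per-day rate, using the same two groups.

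Section 8.7.d (Analysis of Secondary Endpoints) applies that split to a list of outcomes that ends: "30-day readmissions (all-cause and COPD/Asthma exacerbation), and 30-day survival will be compared between patients who were and were not readmitted". The tests for the list are given as "using t-tests or chi-square tests (or Wilcoxon Rank Sum tests and" Fisher's exact tests. A separate paragraph of 8.7.d compares the study cohort with the historical cohort, including the rate of rehospitalization.

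Section 8.7.d does not say which readmissions define the groups. Section 5.2.6 describes the ascertainment without limiting it by cause: "Medical Charts will be reviewed to assess if the subject was readmitted within 30 days of discharge". Section 9.2 describes the follow-up telephone call in the same way.

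**The concern.** There are two separate errors.

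- **Test for the primary count.** The signed rank test ranks within-pair differences, or differences from a fixed value. Here each patient is in exactly one group, and nothing in the plan pairs a readmitted patient with a non-readmitted one. The test does not fit the design. It is also the only hypothesis test that 8.7.c names for the count itself; the Poisson model addresses the per-day rate.
- **Readmission by readmission status.** In 8.7.d the variable that forms the groups is also an outcome. At least one cell of the table is empty by construction, so the null hypothesis of equal proportions is false before any data are seen.

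If the plan were followed literally, the first analysis could not be run. The second would attach a p-value to a contrast that says nothing about the treatment or about predictors of readmission. Otherwise the analyst must depart from the plan after seeing the data.

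**Working it through.** The plan states no power, alpha or expected readmission rate for these comparisons, so there is no figure of its own to reproduce. Both errors are structural. The numbers below only illustrate them.

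**Inputs**

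- Enrolment: 80 (8.7.b).
- Expected 30-day follow-up: 80% (section 4.a), so 80 × 0.80 = 64 patients. N therefore runs from 64 to 80.
- 30-day readmission: not given; assumed 15–25%. With N = 64 this gives about 10 to 16 readmitted; with N = 80, 12 to 20. The groups then range from 10 v 54 to 20 v 60.
- Share of readmissions due to COPD/asthma: not given; varied below.

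**1. Signed rank test**

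The test needs n pairs (x_i, y_i). Groups of 10 and 54, or of 20 and 60, supply none. In a check on simulated counts with readmission set at 10%, 20%, 30% and 50%, the signed rank test could not be computed at any unequal split (for example 6/58, 13/51 and 19/45 at N = 64). It returned a value only at an exact half-and-half split, where which patient is paired with which is arbitrary. The rank sum test ran in every case.

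**2. Readmission by readmission status**

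Let *a* be the number readmitted for any cause, *N* the total, and *c* the number of readmissions due to COPD/asthma.

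*Same definition for group and outcome.* The table is a/a v 0/(N − a), that is 100% v 0%. Fisher's exact p = 1/C(N, a), which depends only on group sizes. For 10 v 54 it is 1/C(64, 10) = 6.6 × 10⁻¹²; for 20 v 60 it is 2.8 × 10⁻¹⁹.

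*All-cause grouping, COPD/asthma outcome.* The table is c/a v 0/(N − a). The second group is 0% because a patient with no readmission has no COPD/asthma readmission. When fewer than half are readmitted, Fisher's two-sided p = C(a, c)/C(N, c):

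| COPD/asthma readmission: readmitted v not | p |
|---|---|
| 1/10 v 0/54 | 10/64 = 0.16 |
| 1/20 v 0/60 | 20/80 = 0.25 |
| 6/13 v 0/51 | 1,716/74,974,368 = 2.3 × 10⁻⁵ |
| 13/20 v 0/60 | 2.5 × 10⁻¹⁰ |

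Given N and a, the p-value moves only with c. It reflects how many readmissions happened to be COPD/asthma, not a difference between two kinds of patient.

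*COPD/asthma grouping, all-cause outcome.* This is the same table transposed. With c = 6, a = 13 and N = 64 it is 6/6 (100%) v 7/58 (12.1%), again p = 2.3 × 10⁻⁵. The first group is 100% by construction.

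**3. What an informative report would look like**

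With the same illustrative counts and Clopper-Pearson 95% limits (the 2.5% point of Beta(x, n − x + 1) and the 97.5% point of Beta(x + 1, n − x)):

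- all-cause: 13/64 = 20.3% (11.3–32.2%);
- COPD/asthma: 6/64 = 9.4% (3.5–19.3%).

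**The case against.** The signed rank wording is almost certainly a slip. Section 8.7.d names the rank sum test for the same split and again for the historical cohort. Because the signed rank test cannot be run on unequal groups, the error would surface at analysis rather than produce a wrong published result. The contrast by readmission status also serves none of the objectives in section 2. All of this is fair and is why the effect is small. It does not make the text right: the plan contradicts itself under its primary endpoint.

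On the second error, one can say that only the same-definition table is fully determined. In the mixed-definition tables a single cell is fixed, the p-value varies with the data (0.25 to 2.5 × 10⁻¹⁰ above), and the free percentage, such as 6/13, usefully describes the share of readmissions due to COPD/asthma. That stands as a limit on the claim: the result is wholly fixed only when the definitions match. But a useful description is not a useful test. With one group held at 0% or 100%, the comparison between groups asks nothing.

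It is also true that the readmission rate and cause split used here are in no document, and that very small p-values do not measure harm. The conclusion does not rest on them.

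**Conclusion.** Both points hold. Section 8.7.c names a paired test for two independent groups, and 8.7.d tests readmission against itself. These are errors in the text, not missing detail, and should be corrected.

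Their reach is modest. Neither error affects the median and per-day mean of PRN treatments, the robust Poisson rate ratio or the historical-cohort comparison of rehospitalization. The structural conclusion needs no assumption; only the illustrative counts rest on an assumed 15–25% readmission and an assumed cause split.

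A lesser point goes with this: the cause-specific readmission outcome has three names. It is respiratory in sections 2.d and 8.7.a ("30-day re-admissions (all-cause and respiratory), 30-day survival, cost of respiratory therapy, and QOL score"), COPD exacerbation in the synopsis and 8.2, and COPD/asthma exacerbation in 8.7.d. Neither error depends on it, but it leaves the cause-specific table undefined.

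**What to change.** - **8.7.c:** replace the signed rank test with the Wilcoxon rank sum (Mann-Whitney) test.
- **8.7.d:** delete 30-day readmission, both all-cause and cause-specific, from the outcomes compared by readmission status. Keep the historical-cohort comparison of rehospitalization.
- **Reporting of readmission:** give all-cause and cause-specific readmission as proportions. The opening of section 9 already provides for this ("Categorical variables will be reported as frequencies and percentages"), and 8.7.e sets the missing-data rule ("subjects with missing data will be excluded in the calculation of percentages"). Add exact 95% confidence intervals; this is an improvement rather than the correction of an error. State the denominator, including how patients withdrawn before discharge are counted, since 5.2.6 starts their 30 days at withdrawal.
- **Definitions:** confirm that the groups are defined by all-cause readmission, which is the plain reading of 5.2.6, 8.7.c and 9.2. Use one cause-specific term in the synopsis and in sections 2.d, 8.2, 8.7.a and 8.7.d.

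The cost is an amendment to wording in section 8.7 and the endpoint lists. No extra data or patients are needed, and no sample size or power figure changes, because none is stated for these comparisons.

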## 2. OBJECTIVES & ENDPOINTS

### a. Primary Objective

1. To establish the requirements for PRN respiratory therapy treatments in patients hospitalized with the diagnosis of COPD exacerbation receiving once-daily ICS/LABA/LAMA (fluticasone furoate/umeclidinium/vilanterol) therapy.

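### The Wilcoxon comparison of PRN use by readmission status uses total counts, so it mixes daily need with length of stay, and the plan does not say whether it or the per-day rate ratio is interpreted

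*Combined protocol and SAP*

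**What the plan says.** The primary objective (section 2.a) is descriptive: "To establish the requirements for PRN respiratory therapy treatments in patients hospitalized with the diagnosis of COPD exacerbation receiving once-daily ICS/LABA/LAMA". It states no hypothesis about two groups.

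Section 8.7.c summarises the endpoint in two ways: the total over the stay, as a median with quartiles, and "as the average number of PRN respiratory treatments per inpatient day". It then compares patients readmitted within 30 days with those who were not, also in two ways:

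- A rank test on the total; the comparison "will be made using a Wilcoxon signed rank test for the number of PRN respiratory treatments".
- A rate ratio, introduced by "Additionally, the incident rate ratio of the average per-inpatient" and completed by the statement that per-day "PRN treatments will be estimated using a robust Poisson regression model comparing patients who were readmitted within 30-days to those who were not".

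Neither comparison is ranked above the other, and no significance level is given.

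Section 8.7.d lists length of stay among the secondary endpoints to be compared between the same two groups; that list ends with "30-day survival will be compared between patients who were and were not readmitted using t-tests or chi-square tests". For the historical cohort, the same section compares PRN use per patient day and takes length of stay as a separate item, "2) length of stay in the hospital".

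**The concern.** A patient in hospital for 7 days has more opportunities for a PRN treatment than one in for 3. The rank test has no exposure term, so it responds to a difference in stay as well as to a difference in daily need. The plan cannot take equal stays for granted, because it sets out to compare stay between these groups.

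At stake is how the result is read. The objective concerns PRN requirements, so a significant rank test on totals invites the statement that readmitted patients needed more PRN treatment. That statement could appear when they needed the same amount per day and only stayed longer. If the rate ratio then shows no difference, the plan gives no rule for which result to report as the finding.

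**Working it through.** **Figures in the plan.** No significance level, power, effect size, length of stay, PRN rate or readmission rate is stated, so there is no statistical figure to reproduce. The accrual arithmetic in section 4.a agrees: 120 × 2/3 = 80 enrolled. With 30-day follow-up in 80%, 80 × 0.80 = 64 patients have a known readmission status.

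**Why totals mix two things.** Expected total = daily rate × days. At 2 treatments per day in both groups, a mean stay of 4 days gives 2 × 4 = 8 and a mean stay of 6 days gives 2 × 6 = 12. The totals differ by half although daily need is the same.

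**Inputs assumed for the simulation (none is in the documents).**
- Readmission 20%: 0.20 × 64 = 12.8, so 13 readmitted and 64 − 13 = 51 not.
- Two-sided 5% level.
- Mean stay 4 days in the non-readmitted, and 5, 6 or 7 days in the readmitted; gamma distribution with shape 4 and a minimum of 1 day.
- The same true rate in both groups, 1 to 3 treatments per day.
- Poisson counts with gamma variation between patients, variance 0.2 to 1.0.

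The rank-sum form was used throughout. A signed rank test needs pairs and cannot be run on independent groups of 13 and 51.

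**Proportion of simulated trials with p < 0.05 when daily need is equal.**

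| Mean stay, readmitted vs not | Rank-sum on totals |
|---|---|
| 5 vs 4 days | about 8–16% |
| 6 vs 4 days | about 15–39% |
| 7 vs 4 days | about 24–60% |

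Over the same settings, a rank-sum test on each patient's treatments per day rejects in about 3–6%. The robust Poisson rate ratio, with days as exposure, rejects in about 7–11%. Neither rises with the difference in stay. The Poisson excess over 5% reflects a sandwich variance estimated from only 13 readmitted patients.

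**Second set of assumptions.** This set used lognormal stays with coefficient of variation 0.4–0.6, 64 or 80 patients, 20–30% readmitted, 0.5–2 treatments per day and between-patient variance 0.1–1.0. The test on totals rejected in 4–6% at equal stays, 8–20% at a stay ratio of 1.25, 15–53% at 1.5 and 36–94% at 2.0. The robust Poisson ratio stayed at about 6–10%. The pattern is the same. The wide ranges show how strongly the size depends on between-patient variation: with 64 patients, 20% readmitted, 2 treatments per day and a ratio of 1.5, it is 30% at variance 0.25 and 15% at variance 1.0.

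**The case against.** The strongest reply is that the same paragraph already handles stay. It plans a per-day summary and a per-day rate ratio for the same two groups, and section 8.7.d compares stay directly, so a count difference driven by stay would be visible beside the other results. This is largely right: a reader might infer that the primary analysis ignores length of stay, and the documents do not support that. What remains is that the rate ratio is added to the count test without replacing it, nothing says which governs, and the rate ratio alone is mildly liberal in groups this small.

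Second, the count test is not wrong on its own terms. If readmitted patients stay longer, their totals really are higher, and total use matters for utilization and for the exploratory cost objective. This stands. A rejection misleads only when it is read as a difference in daily need.

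Third, a reader might infer that the type I error of a confirmatory primary test is inflated. The documents do not support that either: the objective is descriptive, no level is set, and neither comparison is called the primary test.

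Finally, nothing in the documents shows that readmitted patients stay longer. The historical-cohort item in 8.7.d does not show it, because it concerns a different comparison. The plan's intention to compare stay by readmission status shows only that a difference is considered possible.

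**Conclusion.** The point holds in a limited form. The rank test in 8.7.c mixes daily PRN need with length of stay, and the plan does not say whether that test or the per-day rate ratio is interpreted. Under the assumed inputs, equal daily need gives a significant count test in about 8–16% of trials at 5 versus 4 days and 15–39% at 6 versus 4, against 3–6% for a rank test on treatments per day.

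The tempting stronger statement is that a longer stay by itself produces a significant difference. It does not follow: at these moderate differences most simulated trials are not significant, and at equal stays the test on totals keeps close to 5%. The size rests on assumed stays, PRN rates, between-patient variation, readmission rate and significance level. The direction rests only on total = rate × days.

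**What to change.** Change the comparison sentence in 8.7.c so that it does three things:

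1. Applies a Wilcoxon rank-sum test to each patient's PRN treatments divided by inpatient days at risk. The groups are independent, and 8.7.d already names rank-sum for this grouping. Days at risk should be the days over which PRN treatments are recorded, so that patients withdrawn before discharge contribute a matching numerator and denominator.
2. Names the per-day comparison as the one interpreted for PRN need. The robust Poisson rate ratio, with inpatient days as exposure, stays as the estimate of size.
3. Reports total counts descriptively, as a measure of utilization.

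The cost is one changed sentence and the loss of a formal test of total use. No new data are needed: section 5.2.4 already has the number and time of PRN treatments collected daily, and length of stay is already an endpoint.

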### b. Secondary Objectives

1. To measure the distribution of inspiratory flow rates with an InCheck Dial device set on measuring PIF using the medium low resistance setting in patients admitted with COPD exacerbations at Baylor University Medical Center, Dallas TX at the time of enrollment and day of discharge.
2. To determine the hospital length of stay for patients admitted with the diagnosis of COPD exacerbation.
3. To monitor and report any side effects from using once-daily ICS/LABA/LAMA or PRN therapy.
4. To evaluate the transition of care in delivering respiratory therapy medications from hospital to home.
5. To compare the number of PRN treatments, length of hospital stay, and rate of readmissions with findings in a previously analyzed historical cohort of 60 patients in our healthcare system.

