#### 4. PATIENT POPULATION

**a. Enrollment Goal**

This study aims to enroll 80 subjects. With an anticipated acceptance rate of 2/3, this means we will approach 120 eligible candidates over that period. We estimate we will be able to achieve 30-day follow-up in 80% of enrolled patients.

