### **b. Sample Size & Accrual Rate**

Enrollment of 80 patients.

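### The robust Poisson comparison of PRN use by readmission status (Section 8.7.c) has no small-sample correction; with about 13–16 readmitted patients (20% assumed), a conventional 5% test would reject about 7–12% of the time

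*Combined protocol and SAP*

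**What the plan says.** Section 8.7.c first summarises PRN treatments descriptively (median with quartiles, and mean per inpatient day with standard deviation). It then compares patients by 30-day readmission in two ways: a Wilcoxon test on the number of treatments, and a rate ratio that "will be estimated using a robust Poisson regression model comparing patients who were readmitted within 30-days to those who were not". Beyond the word robust, nothing is said about the variance.

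The figures that bear on group size are:

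- Section 8.7.b: "Enrollment of 80 patients".
- Section 4.a: "With an anticipated acceptance rate of 2/3, this means we will approach 120 eligible candidates over that period", and "We estimate we will be able to achieve 30-day follow-up in 80% of enrolled patients".
- Section 8.7.e: "Missing data will not be imputed or carried forward in any of the analyses".

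Section 8.7.d plans a second regression of the same kind, on "the average number of PRN treatments per patient day while hospitalized estimated using a robust Poisson regression model", study cohort against historical cohort. Section 2.b describes the comparator as a "previously analyzed historical cohort of 60 patients in our healthcare system".

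The plan states no expected readmission rate, significance level, sidedness, confidence level or variability of PRN use.

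**The concern.** A sandwich variance is justified in large samples. With a single binary covariate, its accuracy depends on the size of the smaller group, not on the total. Readmitted patients are likely to be a small minority of 64 to 80. PRN counts are skewed and differ strongly between patients, and lengths of stay differ too, so a few patients dominate the rate in the small group. The sandwich estimate is then too small on average, and a normal reference ignores how variable it is.

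At stake is the effect estimate for PRN use and readmission in the primary-endpoint section. Run with common software defaults, the stated method would give an interval that is too narrow, and a chance difference would be reported as an association more often than the nominal level implies.

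**Working it through.** **Plan figures.** 80 ÷ (2/3) = 120 approached, which reproduces Section 4.a. 80 × 0.80 = 64 with 30-day follow-up.

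**Assumed, because the plan gives no value.** Readmission 20% (range 10–30%); two-sided 5% test and 95% interval; 1–2 PRN treatments per day; between-patient dispersion k = 0 to 2 (gamma-Poisson counts); stay fixed at 4 days or gamma with mean about 4.5 days.

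**Group sizes.** 64 × 0.20 = 12.8, so 13 against 51. If all 80 have known status, 80 × 0.20 = 16 against 64. At 10% and 30% of 64, about 6 and 19 readmitted.

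**Estimator.** With counts Y, days T and a log T offset, the group rate is r = ΣY/ΣT and the estimate is log r₁ − log r₀. The uncorrected (HC0) variance is the sum over both groups of Σ(Y − rT)² / (ΣY)². HC3 divides each residual by 1 − h, where h = T/ΣT within the group.

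**Simulation with no true association**, 40,000 replicates per scenario; the closed form was checked against a statsmodels Poisson GLM with HC0 (9.8% in 3,000 replicates).

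Uncorrected variance, normal reference:

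| Setting | Rejection at nominal 5% |
|---|---|
| 13 vs 51, k = 0.25–1, varying stay | 8.8–10.3% |
| 13 vs 51, all scenarios | 7.0–11.9% |
| 16 vs 64, k = 1, varying stay | 9.6% |
| 10% readmitted of 64, k = 0.25–1 | 16.5–18.2% |
| 20% readmitted of 64, k = 0.25–1 | 9.2–10.7% |
| 30% readmitted of 64, k = 0.25–1 | 7.6–8.9% |
| 80 study vs 60 historical (Section 8.7.d), k = 1 | 6.4% |

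A second set of assumptions (3 treatments per day, stay of 1 + Poisson(3.5) days, between-patient CV 0.7–1.0, 8,000 trials per setting) gives 14.5–16.2%, 8.8–10.1% and 7.4–7.9% at 10%, 20% and 30% readmission of 64, and 8.5–9.0% at 20% of 80.

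**Why it happens.** At 20% readmission the average robust standard error is 0.893, 0.869 and 0.846 of the true standard deviation for the three values of k. If that shrinkage were the only problem, the critical values would be 1.96 × 0.893 = 1.75 and 1.96 × 0.846 = 1.66, with two-sided normal tails of 8.0% and 9.7%. The simulated 9.2% and 10.7% are a little higher, because the standard error is also variable and the estimate is not exactly normal. Coverage is 100 − 10.7 = 89.3% to 100 − 9.2 = 90.8%.

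**Effect of corrections**, 13 vs 51, 2 treatments per day, k = 1, varying stay:

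| Variance and reference | Rejection |
|---|---|
| HC0, normal | 10.3% |
| HC1, normal | 9.9% |
| HC3, normal | 7.7% |
| HC3, t on 62 df | 7.2% |
| HC3, t on 12 df (smaller group − 1) | 5.2% |

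HC3 with smaller-group df gives 4.2–5.2% for k = 0.25–1 with varying stay, and 3.3–6.3% over all 13 vs 51 scenarios. Under the second set of assumptions, HC3 with Satterthwaite df gives 5.0–6.4% and a permutation test 4.3–5.1% (3,000 trials per setting).

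**The case against.** Much of the case on the other side stands.

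- **The group size is assumed.** A reader might infer that the plan expects 13 readmitted patients. It does not: it gives no readmission rate. Nor is 64 firm, because Section 5.2.6 uses chart review as well as a phone call, so a missed call need not leave status unknown. With all 80 known, however, the inflation is nearly the same (9.6% against 10.3% in the matching scenario).
- **The defective variance is inferred.** A reader might infer that the plan has chosen large-sample standard errors and a 5% test. It says only robust, and states no level. What can be said is that nothing in the text prevents the uncorrected default. The common HC1 adjustment barely helps.
- **The analysis is secondary in purpose.** The primary objective is to establish PRN requirements. PRN use by readmission status is in none of the listed objectives, and no success criterion depends on it. A reader might infer that the primary result is invalid. It is not, because the medians and means per day involve no such test.
- **It is not the only regression on this variable.** The historical comparison in Section 8.7.d uses the same kind of model and serves a stated objective. Its groups are larger, and inflation there is small (6.4%).
- **A Wilcoxon test is also planned.** It is labelled signed rank, which is a paired test. That label is a separate matter and does not alter the interval for the rate ratio.

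What does not stand is the suggestion that only detail is missing. In every scenario tried, at readmission rates from 10% to 30%, the stated method run in the usual way rejected more than 5% of the time.

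**Conclusion.** The concern holds for the association analysis in Section 8.7.c. With 64 to 80 patients of known status and an assumed 20% readmission rate, an uncorrected sandwich test at a conventional two-sided 5% level rejects about 7–12% of the time under no association. The range is about 7–18% over assumed readmission rates of 30% down to 10%. At 20%, and for moderate dispersion (k = 0.25–1), a nominal 95% interval covers about 89–91%.

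The direction is firm. The size depends on the readmission rate, on how far PRN use varies between patients and on the spread of stays, none of which the plan states, so no single figure should be quoted as the plan's error rate. The change should be made because it is cheap and this interval is likely to be published, but the descriptive primary result does not depend on it.

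**What to change.** In Section 8.7.c, keep the rate ratio and specify:

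- the model as treatment counts with a log patient-days offset;
- the confidence interval and p-value both from an HC3 variance with small-sample degrees of freedom (Satterthwaite, or the smaller group's size minus 1), so that they agree;
- the significance level, sidedness and confidence level, and the readmission rate assumed in planning;
- optionally, a permutation p-value as a check, shuffling the readmission label while keeping each patient's count and days together. It tests the broader null that count and stay are both unrelated to readmission, so it should not replace the interval.

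The cost is about one sentence of text and a few lines of code, with no new data. The interval widens. For 13 vs 51 with equal stays and equal variability, the HC3 to HC0 variance ratio is [(1/13)(13/12)² + (1/51)(51/50)²] ÷ (1/13 + 1/51) = 1.147, so the standard error rises by a factor of 1.071. With t on 12 df (2.179 against 1.96) the interval is 1.071 × 2.179 ÷ 1.96 = 1.19 times as wide. With Satterthwaite df of about 18.6 (t = 2.096) it is 1.071 × 2.096 ÷ 1.96 = 1.15 times as wide.
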